**Cash Benefits, Health Care Utilization, and Health
Protocol and Analysis Plan**

November 14, 2022

ClinicalTrials.gov Identifier: NCT05622903

Study Team

[name], MPH, Brigham and Women's Hospital, Harvard Medical School

[name], MPH, Cambridge Health Alliance, Harvard Medical School

[name], Harvard Kennedy School

Table of Contents

Section A. Introduction	3
Section B. Treatment	3
Section C. Randomization and Participant Eligibility	4
Section D. Data, Study Sample, and Outcomes	5
Section E. Statistical Analysis	6
Section F. References	9

A. Introduction

Unrestricted and unconditional cash benefits, sometimes referred to as a basic income, have emerged as a potential solution to several social issues, including poverty, food insecurity, income volatility, and mental illness, with small pilot studies suggesting improvements in these and other outcomes.¹⁻³ It is an old idea for which there has been renewed interest.⁴⁻⁷ In this study, we investigate the effect of basic income on health care utilization, for which there is less evidence and little to none from a randomized study design.⁸⁻¹¹ Theoretically, a cash benefit could increase health care utilization by improving access, or it could decrease health care utilization by improving health. The effect of a cash benefit on health care utilization is therefore an empirical question.

Using data from the Chelsea Eats program, we propose to study a randomized controlled trial in which the City of Chelsea, Massachusetts held a lottery to allocate cash benefits to its residents for ten months during the first two years of the COVID-19 pandemic.¹² We will analyze the impact of the cash benefit on health care utilization and health. This proposal and analysis plan detail the intervention, randomization, and data source. Importantly, while this analysis plan is specified after the conduct of the trial, it does pre-specify the outcomes and statistical analysis prior to analysis of the data. No analyses of post-intervention outcomes were conducted prior to gaining access to the data.

B. Treatment

Chelsea, Massachusetts, a city of 40,000 people just north of Boston, was among the places in the country hardest hit by COVID-19, both from a health and an economic perspective. Its heavily Latino population is concentrated in sectors of the economy that were shut down when the pandemic hit, and Chelsea residents are also disproportionately likely to be front-line service workers exposed to infection risk.¹³ In April 2020, local community organizations and the City of Chelsea responded to the economic crisis facing jobless Chelsea residents by mounting an unprecedented food distribution effort.

In September 2020, after five months of running its food distribution sites, the City redirected its efforts toward distributing financial support so that residents could purchase their own food through a program called Chelsea Eats. By combining city general revenue funds, state aid, and philanthropic contributions, the City assembled enough resources to distribute Chelsea Eats debit cards to approximately 2,000 households and to replenish the cards on a monthly basis for a total of six months, that was later extended to ten months. The card amounts vary with household size. Most households received \$400 per month, but one- and two-person households received \$200 and \$300, respectively. Spending from the cards was not restricted to food but could be spent on anything and anywhere Visa was accepted. In total, 3,615 households applied for the cards, and 2,074 were chosen to receive the cash assistance cards via a lottery. The debit cards were credited with the first payment on November 18th, 2020 and the second payment on December 18th, 2020. The program continued with monthly credits through August 2021.

C. Randomization and Participant Eligibility

Between July 27, 2020 and August 17, 2020, the City accepted applications for the Chelsea Eats cash assistance cards. Multilingual information about the cards was distributed to individuals using the city-run food distribution sites. Additionally, information and applications were disseminated to community-based organizations, food pantries, faith groups, health care organizations, and low- and moderate-income housing complexes. Direct outreach to residents by city staff occurred in multiple locations, including food pantry lines, COVID-19 testing lines, and social service agencies. Applications could be submitted online via the city's website or on paper by dropping them off or mailing them to City Hall. In practice, most applications were submitted by residents attending one of the various city or community partner food pantries, where city staff, equipped with tablets, assisted residents with the application.

Eligibility criteria included:

- Resident of Chelsea, Massachusetts
- Household income at or below 30% of the U.S. Department of Housing and Urban Development's Area Median Income

The lottery was a weighted lottery. Specifically, a household could receive additional lottery tickets by meeting any of the following criteria:

- No one in the household was currently working
- The household was not receiving unemployment insurance
- The household was not receiving food assistance (e.g., SNAP benefits)
- There was a disabled household member
- There was a household member over 65 years of age
- There was a household member who was a veteran
- There was a household member who was under 6 years of age
- There was a household member between the ages of 6 and 17

The total number of lottery tickets per application ranged from 1 to 8. Although it was the city's intention to restrict households to a single application, some households managed to enter the lottery with more than one application. In these cases, the household still received only a single Chelsea Eats card. Records for the duplicate applicants will be combined into a single record, summing the lottery tickets across the duplicate records to determine the household's overall probability of winning the lottery. We account for the differential probability of winning the lottery across households in the statistical analysis (see section E.2).

Of note, some households never picked up their Chelsea Eats cards. The city then gave these unused cards to households from a randomly generated waitlist that was created at the time of random assignment. All waitlisted households ultimately received Chelsea Eats cards and are therefore part of the treatment group. The waitlist households received their cards approximately one month later than the primary lottery winners, but the cards were credited with both the

payments for the first and second months – so the total payments received by waitlist households are the same as initial lottery winners.

D. Data, Study Sample, Outcomes, and Other Variables

D.1. Data and Study Samples

The two closest emergency departments to the City of Chelsea are Cambridge Health Alliance’s Everett Hospital and Massachusetts General Hospital. Participants in the study will be matched to their electronic health record at Cambridge Health Alliance (CHA) and Mass General Brigham (MGB) using a probabilistic algorithm based on name, year of birth, gender, address, and phone number.

There are two additional/secondary study samples. The first will be a subsample of study participants who received their primary care at CHA or MGB at baseline. The second will be children of the participants, identified using address and phone number of the participants as well as dependency relationships available through the electronic health record data.

D.2. Planned Outcomes

Outcomes will be assessed on a per-household basis and measured using the electronic health record data over the ten months of the trial.

1. Primary Outcome

a. Emergency department use

- i. We will use the electronic health record data to count visits to the emergency department. Our primary outcome will be assessed on a monthly basis over the duration of the cash benefit and is therefore specified as a frequency variable.
- ii. We will also characterize the nature of these visits including by pre-specified diagnosis categories and whether it resulted in a hospital admission, as secondary outcomes (see below).
- iii. Our primary outcome is count-based and not binary (i.e., any versus none) in order to maximize power. To understand general access to emergency department care versus intensity in emergency department use, we will separately assess a dichotomized version of the outcome.

2. Secondary Outcomes

a. Emergency department use by pre-specified categories:

- i. Behavioral health-related ED visit
- ii. Substance use disorder-related ED visit
- iii. Potentially avoidable vs non-avoidable (categorized using the previously validated New York University algorithm)

- iv. Resulting in admission to the hospital
- v. As above, we will separately assess count-based and binary versions of these outcomes.
- b. Outpatient service use
 - i. Outpatient service use includes office visits and other types of outpatient care such as imaging and procedures. We will also assess outpatient service use disaggregated according to type of service (i.e., office visits to primary care, cancer screening tests).
 - ii. As above, we will separately assess count-based and binary versions of these outcomes.
- c. COVID vaccination
 - i. The first COVID vaccine received emergency use authorization on December 11, 2020. Vaccination status will be a binary variable for having received at least one dose of any COVID vaccine by the end of the trial period.
- d. Clinical measures: hemoglobin A1c, blood pressure, weight, and cholesterol
 - i. These are continuous measures available in the electronic health record. We will use the latest available reading or result during trial period.
 - ii. Given potential changes in access to care (see outcomes above) that could affect the set of participants for whom we have data for these measures, we have also specified a sensitivity analysis below using the subsample for patients who received their primary care at CHA or MGB at baseline.

D.3. Patient Characteristics

The data includes information on participants' household size, disability status, veteran status, work status, income, receipt of other benefits or assistance, and utilization/spending prior to randomization. These characteristics come from the lottery application form or electronic health records and are assessed prior to randomization. In the event that there are high levels of missingness for any key covariate (i.e., >2%), multiple imputation methods will be used.

E. Statistical Analysis

E.1. Evaluation of randomization, balance, and attrition

We will test for balance between treatment and control based upon observable baseline characteristics for the overall study population.

Because differential attrition correlated with treatment, for example due to death, could introduce bias into our results, we will also evaluate the attrition rate and assess for balance between treatment and control based upon both baseline characteristics for the final analytic sample (and attriters) and potential causes of attrition.

E.2. Statistical specification

Our primary analytic approach is an analysis based on the intent-to-treat principle that compares outcomes for those randomized into the treatment group to those who were randomized into the control group. Specifically, we will estimate the following linear regression model:

$$y_i = \beta_0 + \beta_1 \text{CASH}_i + \beta_3 \mathbf{X}_i + \epsilon_i,$$

where y_i is the utilization or clinical outcome for individual or household i . See section D.2. for a list of our primary and secondary outcomes. “ CASH_i ” is an indicator for whether individual i won the lottery and was thus randomized into the treatment group. \mathbf{X}_i is a vector of covariates, specifically patient characteristics, including baseline (pre-randomization) values of the outcome variable, which are not explicitly necessary since they should be unrelated to treatment status, but they may increase the precision of our estimates to the extent that they explain some of the variance in the outcome.

The coefficient on CASH_i , β_1 , is our main coefficient of interest; it provides the difference in means between the treatment groups and the control group. In addition to our primary specification above that corresponds to testing for a level shift, we will also include an interaction term between an indicator for time and treatment status to test for changes in slope.

As described in section C, a household could receive additional lottery tickets by meeting specific criteria. Observations will thus be weighted by the inverse probability of winning the lottery so that β_1 is an unbiased estimate of the relationship between winning the lottery and the outcome. An alternative specification that includes indicators for number of lottery tickets is discussed below. Standard errors will be clustered at the household level and adjusted for heteroskedasticity.

E.3. Subgroup analyses

To examine heterogenous effects of the cash benefits, we will repeat our analyses for four pre-specified subgroups, each defined based on data from the pre-randomization period. The subgroups are: (1) chronic disease at baseline, (2) history of acute care utilization, (3) financial distress at baseline, and (4) poor self-reported health at baseline.

Specifically, we use electronic health record data to define participants by whether they have a known chronic disease (e.g., diabetes, hypertension, depression, anxiety) for which she/he/they is prescribed a regular medication. We will also use the electronic health record data to define participants by whether the participant had any acute care utilization in the year prior to randomization.

For a subset of the participants, we have baseline survey data that enables subgroup analyses by level of financial distress and self-reported health. Financial distress is defined as an affirmative answer on a survey question asking the participant whether she/he/they had any bills, expenses,

or needs that they were unable to pay. Poor self-reported health is defined as a positive screening (score \geq 3) on the 2-question version of the Patient Health Questionnaire, a positive screening (score \geq 3) on the 2-question version of the Generalized Anxiety Disorder questionnaire, or a fair/poor response on the 5-point scale of self-rated health.

E.4. Alternative specifications and sensitivity analyses

Our primary specification includes patient characteristics and baseline values of the outcome in the model to improve power as well as any chance imbalance between the study arms after randomization. As described in section E.1., we will compare covariates between the treatment and control groups, and we will explore whether our results are sensitive to inclusion of these covariates in the model. Importantly, our primary specification accounts for differential probability of winning the lottery using inverse probability weights. As an alternative approach, we will include the set of covariates that are correlated with treatment probability into the model, specifically indicators for number of lottery tickets. Finally, as a sensitivity check, we will also conduct our analyses on the subpopulation of participants with established primary care at MGB or CHA at baseline.

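### Does the plan need changing because D.2 sets outcomes per household while D.1 links participants and E.2 allows either unit?

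*Combined protocol and SAP*

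**What the plan says.** D.2 opens with a rule for every outcome: "Outcomes will be assessed on a per-household basis and measured using the electronic health record data over the ten months of the trial". It gives no exception and no rule for combining members. The primary outcome is a monthly count of ED visits, without saying whose.

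D.1 builds the main sample by matching participants to their own CHA and MGB records on personal identifiers. Children are one of two secondary samples: "The second will be children of the participants, identified using address and phone number of the participants". Linkage of other adults is not described.

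In E.2 the outcome "is the utilization or clinical outcome for individual or household" i, while the treatment variable "is an indicator for whether individual i won the lottery". Covariates are patient characteristics, "including baseline (pre-randomization) values of the outcome variable". On variance, "Standard errors will be clustered at the household level".

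Section C draws the lottery by household and merges duplicate applications into one record. D.2 words vaccination and the clinical measures as one person's values, and its remark on selective availability of the clinical measures refers to participants.

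**The concern.** There is one primary outcome, tested at two-sided 0.05 without adjustment, in a plan written after the trial was run. If its unit is open, the prespecification looks incomplete. Three consequences would be in play.

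- **Meaning.** A household vaccination variable depends on an unstated rule. With an assumed 60% uptake per person and three independent members, *any member vaccinated* gives 1 − 0.4³ = 93.6% and *all members vaccinated* gives 0.6³ = 21.6%. A household's latest A1c could come from a different person than its baseline value, and could differ between arms merely because cash changed who was tested.
- **Power.** The number of households is fixed, so counting one person per household may discard visits that the planned child linkage could supply.
- **Dose.** Section B pays $200, $300 or $400 for one, two, or three or more people. That is $200, $150 and at most $133 per person, so weighting by person or by household averages over different amounts of cash.

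The apparent remedy is to make the primary count a household total over the applicant and linked children, and to move vaccination and clinical measures to the individual.

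**Working it through.** The documents give no power, visit rate, SD or within-household correlation, so there is no figure of the plan's own to reproduce.

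**1. How far the two units differ.** Under D.1 the main sample holds matched participants. If a participant is the applicant, a household contributes one linked person, and *individual i* and *household i* are the same row. The exception is merged duplicates, whose number is not given. Duplication arises at application, before the lottery, and the summed tickets enter the weights, so it does not favour either arm. E.2's individual unit and household clustering still have a use: several children per household in the secondary sample, and repeated household-months. The intent-to-treat rule, which "compares outcomes for those randomized into the treatment group to those who were randomized into the control group", points to the same randomised households under both readings.

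**2. Vaccination and clinical measures.** A switch between members needs more than one linked member. Under D.1 there is none in the main sample outside merged duplicates. The latest reading and the baseline value are then the participant's own, which E.2 permits.

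**3. Power of a wider total.** Inputs from section B: 3,615 households, 2,074 winners, hence 3,615 − 2,074 = 1,541 controls. Ignoring weights and non-matches, the effect giving 80% power on a one-person count, in SD units, is

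d = (1.960 + 0.842) × √(1/2,074 + 1/1,541) = 2.802 × 0.03363 = 0.094.

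For a total over m people with within-household correlation ρ (both assumed), the SD relative to one person is r = √(m(1 + (m − 1)ρ)). Power is Φ(2.802 × k/r − 1.960), with k = m if all respond equally and k = 1 if only the applicant responds. The total breaks even when other members' effect, as a fraction of the applicant's, is f = (r − 1)/(m − 1).

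| m | ρ | r | Power, all respond | Power, applicant only responds | Break-even f |
|---|---|---|---|---|---|
| 2 | 0.05 | 1.449 | 0.972 | 0.489 | 0.45 |
| 2 | 0.5 | 1.732 | 0.899 | 0.366 | 0.73 |
| 3 | 0.2 | 2.049 | 0.984 | 0.277 | 0.52 |
| 4 | 0.05 | 2.145 | 0.999 | 0.257 | 0.38 |
| 4 | 0.5 | 3.162 | 0.943 | 0.141 | 0.72 |

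The total therefore wins or loses depending on an effect in other members that the documents do not give. Section A says that cash could raise or lower utilization, so adult and child effects need not agree.

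**4. Dose weighting.** Take a one-person household ($200 per person) and a four-person household ($400/4 = $100). Weighting by household gives (200 + 100)/2 = $150; weighting by person gives (1 × 200 + 4 × 100)/5 = $120. If members have similar visit rates, the relative effect on a household total is also weighted by person. The dose argument thus counts equally against a household total; a one-person count is what weights households equally.

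**5. Error rate.** Either unit, fixed in advance, tests at 5%. Suppose instead that the choice between an applicant count and a wider count were made after seeing results. With test statistics correlated 0.58 to 0.95 (from simulation under assumed rates), the chance of at least one P < 0.05 under the null would be about 8.8% down to 6.5%. The two readings in step 1 differ only in merged duplicates, so their correlation should be much closer to 1 and the inflation correspondingly smaller.

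**The case for a change.** The strongest case is that D.2 names the household without qualification, and the lottery, card, tickets and merged records are all at household level. An applicant-only count leaves that sentence inaccurate for households with other members. The benefit goes to the household, so some response by others is plausible, and the child linkage is already planned. A simulation of the weighted lottery under assumed visit rates, with children sharing the applicant's relative effect, puts the difference detectable with 80% power at 21–26% for the applicant alone and 15–22% with children added. Its break-even relative effect for children is about 0.3 to 0.6.

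The textual mismatch stands: nothing says whose visits are counted. The preference for a wider total does not follow from it. D.1 deliberately makes children a secondary sample, and moving them into the primary outcome would override that choice. The power rationale in D.2 explains a count rather than an any-or-none outcome and is silent on whose visits enter. The gain depends on assumed rates and a shared effect. With no linkage of other adults described, the result would still be only part of the household.

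**Conclusion.** No change to the plan follows. The inconsistency between D.1, D.2 and E.2 is a gap in wording that analysts can fill sensibly: one record per randomised household, using the matched participant's visits, and that person's own vaccination status, clinical readings and baseline values. Describing the primary outcome in the report as CHA/MGB visits of the linked persons, and noting how merged duplicates were handled, would make this plain.

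A wider household total is a fair alternative, with power anywhere from 14% to over 99% where the one-person count has 80%, depending on how other members respond. It is not shown to be better.

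This rests on three points: participant means applicant (an inference), merged duplicates are few (their number is not given), and the unit is settled before outcomes are compared between arms. The power and vaccination figures are illustrations under stated assumptions, not estimates for this trial.

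### The E.2 weight, 1/P(winning) for every observation, cannot make β1 unbiased: no weight is stated for the control arm

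*Combined protocol and SAP*

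**What the plan says.** Section C describes a weighted lottery: 1 to 8 tickets per application, earned through eight criteria such as nobody working, no food assistance, a disabled member or a child in a given age band. Duplicate applications are merged and their tickets summed. Section B gives 3,615 applicant households and 2,074 winners.

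Section E.2 handles the unequal chances with one rule: "Observations will thus be weighted by the inverse probability of winning the lottery". Winners and non-winners are not distinguished. The benefit claimed for this rule is that the coefficient on the lottery indicator "is an unbiased estimate of the relationship between winning the lottery and the outcome". The same section describes the covariates X as terms "which are not explicitly necessary since they should be unrelated to treatment status", there only for precision.

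Section E.4 repeats that "our primary specification accounts for differential probability of winning the lottery using inverse probability weights", without a formula, and confirms that "Our primary specification includes patient characteristics and baseline values of the outcome in the model". It plans two relevant checks. On covariates, "we will explore whether our results are sensitive to inclusion of these covariates in the model". On tickets, "As an alternative approach, we will include the set of covariates that are correlated with treatment probability into the model", in the form of ticket-count indicators.

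Section E.1 says: "We will test for balance between treatment and control based upon observable baseline characteristics for the overall study population". It does not say whether those tests are weighted.

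**The concern.** Tickets drive the chance of winning, and the things that earn tickets (work status, disability, age of members, benefit receipt) may well relate to ED use. The weight is the only device E.2 relies on to remove that confounding. A weight that is a function of tickets alone, and the same function in both arms, cannot remove it. The weighted winners then match the applicant pool, while the weighted non-winners are pushed toward low ticket counts.

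Three things follow.

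- The estimate without covariates would carry the full bias, and its difference from the adjusted estimate could be taken for sensitivity to covariates.
- Balance tests run unweighted, or with the written weight, would show large gaps on the ticket criteria after a perfectly fair draw, and could be taken for failed randomization.
- The remark that X should be unrelated to treatment is true only in a correctly weighted sample, because several of the items in D.3 earn tickets.

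**Working it through.** **Algebra.** Take n households in a ticket stratum with probability p of being in the treatment group.

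- Weight 1/p in both arms: treated mass n·p·(1/p) = n; control mass n·(1−p)·(1/p) = n(1−p)/p. The odds are p/(1−p), the same as unweighted.
- Weight 1/p for treated and 1/(1−p) for control: both masses equal n, so ticket counts balance.

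This needs no assumption beyond p varying with tickets, which is the purpose of the lottery design. The plan states no figure that could be reproduced here.

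**Size of the imbalance.** From Section B, mean p = 2,074/3,615 = 0.574. From Section C, tickets run from 1 to 8. The ticket distribution is not given, so three are assumed. I approximate p(t) = 1 − exp(−λt) and solve λ for mean p = 0.574. For uniform tickets λ = 0.216, so p(1) = 0.19 and p(8) = 0.82, with odds from 0.24 to 4.63.

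Under the written weight, control mass is proportional to (1−p)/p. For uniform tickets, t = 1 to 8, this is 4.15, 1.85, 1.10, 0.73, 0.51, 0.38, 0.28, 0.22 (sum 9.21). One-ticket households therefore hold 4.15/9.21 = 45% of control weight, and the weighted control mean is 22.58/9.21 = 2.45 tickets.

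| Assumed tickets | Mean tickets treated vs control: unweighted | Written weight | Arm-specific | One-ticket share of pool → of control weight (written) |
|---|---|---|---|---|
| Uniform 1–8 | 5.30 vs 3.42 | 4.50 vs 2.45 | 4.50 vs 4.50 | 12.5% → 45% |
| Mostly low (.35, .25, .15, .10, .06, .04, .03, .02) | 3.23 vs 1.77 | 2.61 vs 1.47 | 2.61 vs 2.61 | 35% → 70% |
| Centred (.05, .12, .22, .25, .18, .10, .05, .03) | 4.46 vs 3.47 | 4.04 vs 2.92 | 4.04 vs 4.04 | 5% → 21% |

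A simulated draw without replacement, over four assumed ticket shapes, agrees. The written weight leaves the gap in mean tickets about as large as no weighting, or larger (for example 2.06 against 1.90 for uniform tickets). Arm-specific weights leave at most 0.01 ticket.

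**Effect on the estimate.** Monte Carlo with a true effect of zero: 2,000 replicates, 3,615 households, 2,074 drawn without replacement with chance proportional to tickets, weighted least squares, heteroskedasticity-robust standard errors. All of the following are assumed:

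- Prevalences: not working .45, no unemployment insurance .65, no food assistance .50, disabled .15, over 65 .15, veteran .02, child under 6 .30, child 6–17 .45.
- Tickets = 1 + criteria met, capped at 8.
- Mean 0.5 ED visits per 10 months, gamma-Poisson counts, baseline/follow-up correlation 0.27 to 0.28.
- Each criterion multiplies ED use by the same factor.
- X = the ticket items that D.3 names, household size and baseline ED count. Income is not modelled.

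Bias as % of mean ED use (type I error in brackets):

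| Analysis | Criterion +10% | Criterion +20% |
|---|---|---|
| No covariates, no weights | +5.7 (14%) | +10.7 (37%) |
| No covariates, written weight | +6.4 (17%) | +11.7 (44%) |
| No covariates, arm-specific weights | 0.0 (4%) | 0.0 (6%) |
| Planned X, written weight | +1.0 (4.3%) | +1.6 (6.6%) |
| Same, weak persistence (correlation 0.06 to 0.07) | +1.3 (5.8%) | +2.0 (6.0%) |
| Same, 5% of households with doubled tickets | +0.8 (4.5%) | +1.8 (5.6%) |

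Monte Carlo standard error is 0.14 to 0.17 points for bias and about 0.5 points for type I error. With all eight criteria in X, the written weight gives −0.5 to 0.0 points. Arm-specific weights or ticket indicators stay within 0.4 points of zero in every run, with type I error of 4% to 6%. If ED use is unrelated to tickets, the bias is zero.

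**Balance tests.** Seven of the eight criteria differ at p<0.05 in 98% to 100% of replicates, both unweighted and with the written weight. With arm-specific weights each criterion differs in 4% to 6%. Arm gaps under the written weight are 13 points for no unemployment insurance, 12 each for not working, no food assistance and child 6–17, 9 for child under 6, and 5 each for disabled and over 65.

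**The case against.** The strongest reply is that the E.2 sentence is shorthand. It states the aim of an unbiased β1, E.4 uses the usual name for the method, and only arm-specific weights achieve the aim. That may be what the investigators meant. It cannot be confirmed from the text, and an analyst who coded the sentence literally would use the wrong weight.

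Second, the primary estimate is hardly harmed, because X removes most of the bias, or all of it if every criterion is included. This stands, and it limits the severity. D.3 is not a closed list, but it names no age-of-member item although three ticket criteria are age-based, and E.2 presents X as dispensable.

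Third, a common gradient for all eight criteria is unfavourable. With mixed signs (assumed +20% for not working, disabled and over 65, +10% for veteran, −10% to −15% for the other four) the no-covariate bias is about −1% and type I error about 5%. This stands too: the larger figures are illustrations and not forecasts.

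Fourth, the planned ticket-indicator analysis would expose the problem, and investigators who know their lottery are unlikely to mistake ticket-driven gaps for failed randomization. In part this is true. But the indicator model ranks as the alternative, so a disagreement would leave the mis-weighted model as primary, and changing the weight after seeing results would weaken the pre-specification.

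**Conclusion.** The concern holds. As written, the E.2 rule does not have the property claimed for it. That follows from algebra and from p varying with tickets, not from any simulated input. Whether the rule is an error or loose wording cannot be settled from the documents.

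The consequences are modest for the headline result and larger for the checks around it. Under the stated assumptions the planned primary model is off by roughly 1% to 2% of mean ED use with near-nominal type I error. The analysis without covariates does no better than one with no weights at all, and balance tests fail almost always on most ticket criteria. The sign of the no-covariate bias follows the gradient: toward more ED visits in the cash arm if the criteria on balance raise ED use, the reverse if they lower it. This should be fixed. Confidence in the sizes is medium, because the ticket distribution and the gradient are both assumed.

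**What to change.** Replace the weighting sentence in E.2 with, for example: *Observations will be weighted by the inverse probability of the arm assigned: 1/p for treatment-group households and 1/(1−p) for control households, where p is the probability of ending in the treatment group, waitlist included, given the household's summed tickets.* Alternatively, move the planned ticket-count indicators into the primary model. If arm-specific weights were always intended, only the wording needs correcting.

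In either case, use the same weights or indicators in the E.1 balance tests and in the E.4 analysis without covariates, and limit the remark about X being unrelated to treatment to the correctly weighted sample.

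The cost is one or two sentences and a line of code, with no new data. There are trade-offs:

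- **Precision.** With covariates and 10% to 20% gradients, the standard deviation of the estimate rises about 2% to 9% with arm-specific weights and about 0.5% to 5% with ticket indicators. If ED use is unrelated to tickets, both are 2% to 3% smaller. Root mean squared error (10% / 20% gradient) is 6.6 / 6.8% of the mean as written, 6.7 / 7.2% with arm-specific weights and 6.6 / 7.0% with indicators. The gain is valid checks and the stated unbiasedness, not a more accurate primary estimate.
- **Extreme weights.** A losing household with 16 summed tickets gets 1/(1−p) = exp(16λ): about 32 if tickets are uniform (λ = 0.216), about 607 under the mostly-low distribution (λ = 0.4006). Such households should be rare, but the plan should say how they are handled. Ticket indicators avoid the problem.
- **Estimand.** If the effect varies with tickets, the indicator model averages it over strata with weights that differ from the applicant pool.
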